10.1 Exposure

Tables with descriptive statistics in accordance with section 7.1 will be presented for the following parameters:

- actual duration ABBVIE REGIMEN (in days);

¹ Note that MLR is possible ONLY if more than one explanatory variables will have a p-value <0.25 in the corresponding univariate logistic regression analysis.

P16-253 (CITRIN) _ STATISTICAL ANALYSIS PLAN _ FINAL 2.0 _ 16 Mar 2018

- the number of patients with collected deviating duration reasons;
- adherence ABBVIE REGIMEN (calculated for Paritaprevir/R-Ombitasvir and for Dasabuvir separately):
 - percentage of target dose taken in treatment intervals (weeks 1-4, 5-8 and 9-12) for Paritaprevir/R-Ombitasvir and for Dasabuvir;
 - percentage of patients who missed of study drug administration for at least 7 days in a row.

All corresponding listings will be presented.

10.2 Adverse events

Only treatment-emergent adverse events will be analyzed.

Treatment-emergent AE is any reported event that begins or worsens in severity after initiation of study drug through 30 days post-study drug dosing.

All analyzed AEs will be coded using the MedDRA version 20.0 (or further updating) and tabulated in the report with grouping by primary system organ class (SOC) and preferred term (PT).

The frequency of a specific AE occurrence will be presented by the proportion of patients with this AE emergence as well as the total number of episodes this AE for a diagnosis.

The following tables with descriptive statistics in accordance with section 7.1 will be presented:

- all AE / SAE;
- AE / SAE by severity;
- AE / SAE by relationship to the study drug.

Tables of AE/SAE by severity (relationship to the study drug) will be prepared using the following rules. Each SOC / PT category will include only the AEs with the highest severity (relationship to the drug) in each patient, while in the Total category all AEs of this patient will be considered. At the same time, each patient will be counted only once with highest severity (relationship to the study drug) in each SOC and each PT level as well as Total level.

Also all AEs will be presented in listings. Additional listings for unintended medication errors will be provided.

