| Total [1] | XX (XX.X) /XX |
| System organ class 1 | XX (XX.X) /XX |
| Preferred term A | XX (XX.X) /XX |
| Preferred term B | ... |
| ... | ... |
| System organ class 2 | ... |
| ... | ... |
| ... | ... |

N: the number of patients in the safety population.

n: the number of patients who have AE with appropriate SOC/PT. Percentages are calculated as (100 x n/N).

E: the number of AE episodes, which have an appropriate SOC and/or PT.

Patients with several AEs having the same SOC and PT are accounted only once for appropriate SOC and PT.

[1] The Total line displays the number (n) and the proportion (%) of patients who have at least one AE as well as the total number of AE episodes in the study.

The coding is carried out by the dictionary MedDRA v.20.0.

The table does not include AEs that occurred prior to the first intake of the study drug.

The data is sorted alphabetically: first by SOC, then by PT.

Program code, date, time

Data extracted: DD.MM.YYYY

Similar to table 3.2.1, table 3.2.2 will be constructed:

P16-253 (CITRIN) _ STATISTICAL ANALYSIS PLAN _ FINAL 2.0 _ 16 Mar 2018**Table 3.2.2 Serious adverse events**

P16-253 (CITRIN) _ STATISTICAL ANALYSIS PLAN _ FINAL 2.0 _ 16 Mar 2018

AbbVie LLC

P16-253 (CITRIN)

Table 3.2.3 Adverse events by relationship to the study drug

The safety population

Page X of X

| System Organ Class (SOC) Preferred term (PT) | Relationship to the study drug | Total (N=XX) n (%) /E |
|---|--|---|
| Total [1] | Reasonable possibility No reasonable possibility Total | XX (XX.X) /XX XX (XX.X) /XX XX (XX.X) /XX |
| System Organ Class 1 | Reasonable possibility No reasonable possibility Total | XX (XX.X) /XX XX (XX.X) /XX XX (XX.X) /XX |
| Preferred term A | Reasonable possibility No reasonable possibility Total | XX (XX.X) /XX XX (XX.X) /XX XX (XX.X) /XX |
| Preferred term B | Reasonable possibility ... | XX (XX.X) /XX ... |
| System Organ Class 2 | Reasonable possibility ... | XX (XX.X) /XX ... |

N: the number of patients in the safety population.

n: the number of patients who have AE with appropriate SOC/PT. Percentages are calculated as (100 x n/N).

E: the number of AE episodes, which have an appropriate SOC and/or PT.

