Each SOC/PT category includes only AEs with the highest relationship to the study drug in each patient. Each patient is counted only once in the Total lines and in the lines for each SOC or SOC/PT categories. Thus, if patient has several AEs with the same SOC and PT but different relationship to the drug, only the AEs with maximum relationship will be accounted, while each patient will be accounted only once in line which corresponds the highest relationship of his AEs.

[1] The Total lines displays the number (n) and the proportion (%) of patients who have AEs. Each patient is counted once in line which corresponds the highest relationship of all his AEs. #E displays the number of all AEs episodes with appropriate relationship to the drug in the study.

The coding is carried out by the dictionary MedDRA v.20.0. The table does not include AEs that occurred prior to the first intake of the study drug.

The data is sorted alphabetically: first by SOC, then by PT and relationship to the drug.

Program code, date, time

Data extracted: DD.MM.YYYY

Similar to table 3.2.3, table 3.2.4 will be constructed:

P16-253 (CITRIN) _ STATISTICAL ANALYSIS PLAN _ FINAL 2.0 _ 16 Mar 2018

Table 3.2.4 Serious adverse events by relationship to the study drug

P16-253 (CITRIN) _ STATISTICAL ANALYSIS PLAN _ FINAL 2.0 _ 16 Mar 2018

AbbVie LLC

P16-253 (CITRIN)

Table 3.2.5 Adverse events by severity

The safety population

Page X of X

| System Organ Class (SOC) Preferred term (PT) | Severity | Total (N=XX) n (%) /E |
|---|----------|-----------------------------|
| Total [1] | Severe | XX (XX.X) /XX |
| | Moderate | XX (XX.X) /XX |
| | Mild | |
| | Total | XX (XX.X) /XX |
| System Organ Class 1 | Severe | XX (XX.X) /XX |
| | Moderate | XX (XX.X) /XX |
| | Mild | |
| | Total | XX (XX.X) /XX |
| Preferred term A | Severe | XX (XX.X) /XX |
| | Moderate | XX (XX.X) /XX |
| | Mild | |
| | Total | XX (XX.X) /XX |
| Preferred term B | Severe | XX (XX.X) /XX |
| | Moderate | XX (XX.X) /XX |
| | Mild | |
| | Total | XX (XX.X) /XX |
| ... | ... | ... |
| System Organ Class 2 | Severe | XX (XX.X) /XX |
| | Moderate | XX (XX.X) /XX |

P16-253 (CITRIN) _ STATISTICAL ANALYSIS PLAN _ FINAL 2.0 _ 16 Mar 2018

| System Organ Class (SOC) Preferred term (PT) | Severity | Total (N=XX) n (%) /E |
|---|----------|-----------------------------|
| | Mild | |
| | Total | XX (XX.X) /XX |
| ... | ... | ... |
| ... | ... | ... |

N: the number of patients in the safety population.

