n: the number of patients who have AE with appropriate SOC/PT. Percentages are calculated as $(100 \times n/N)$.

E: the number of AE episodes, which have an appropriate SOC and/or PT.

Each SOC/PT category includes only AEs with the highest severity in each patient. Each patient is counted only once in the Total lines and in the lines for each SOC or SOC/PT categories. Thus, if patient has several AEs with the same SOC and PT but different severity, only the AEs with maximum severity will be accounted, while each patient will be accounted only once in line which corresponds the highest severity of his AEs.

[1] The Total lines displays the number (n) and the proportion (%) of patients who have AEs. Each patient is counted once in line which corresponds the highest severity of all his AEs. #E displays the number of all AEs episodes with appropriate severity in the study.

The coding is carried out by the dictionary MedDRA v.20.0.

The table does not include AEs that occurred prior to the first intake of the study drug.

The data is sorted alphabetically: first by SOC, then by PT and relationship to the drug.

Program code, date, time

Data extracted: DD.MM.YYYY

Similar to table 3.2.5, table 3.2.6 will be constructed:

Table 3.2.6 Serious adverse events by severity

P16-253 (CITRIN) _ STATISTICAL ANALYSIS PLAN _ FINAL 2.0 _ 16 Mar 2018
Hematology

 AbbVie LLC
 P16-253 (CITRIN)

Table 3.3.1 Hematology. Descriptive statistics

 The safety population
 Page X of X

| Parameter Visit Statistics | Total (N = XX) | Change from baseline (N = XX) |
|----------------------------------|-------------------|----------------------------------|
| Hemoglobin (unit measure) | | |
| Visit 1 | | |
| n | XX | |
| Mean | XX.X | |
| SD | XX.XX | |
| Median | XX.X | |
| IQR | XX.X | |
| Min | XX | |
| Max | XX | |
| EoT | | |
| n | XX | XX |
| Mean | XX.X | XX.X |
| SD | XX.XX | XX.XX |
| Median | XX.X | XX.X |
| IQR | XX.X | XX.X |
| Min | XX | XX |
| Max | XX | XX |
| SVR12 | | |
| n | XX | XX |
| Mean | XX.X | XX.X |
| SD | XX.XX | XX.XX |
| Median | XX.X | XX.X |
| IQR | XX.X | XX.X |
| Min | XX | XX |

P16-253 (CITRIN) _ STATISTICAL ANALYSIS PLAN _ FINAL 2.0 _ 16 Mar 2018

| Parameter Visit Statistics | Total (N = XX) | Change from baseline (N = XX) |
|----------------------------------|-------------------|----------------------------------|
| Max | XX | XX |
| Platelets (unit measure) | | |
| ... | | |
| Prothrombin time (unit measure) | | |
| ... | | |

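### In the AE tables by severity and relationship (3.2.3–3.2.6), the worst-grade rule is applied to the episode count E in the SOC and PT rows, so E there is not the number its footnote defines

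*SAP*

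**What the plan says.** SAP 10.2 promises two measures of frequency for each adverse event: the proportion of patients with it, "as well as the total number of episodes this AE for a diagnosis". For the tables by severity and by relationship it adds a rule about events: "Each SOC / PT category will include only the AEs with the highest severity (relationship to the drug) in each patient". The same sentence then makes an exception at the level of the Total, where nothing is filtered out: "while in the Total category all AEs of this patient will be considered". A separate sentence then says that each patient is counted once, at the highest grade, at SOC, PT and Total level.

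The table shells in SAP section 18 repeat this. For several events with the same SOC and PT, the footnote to Table 3.2.3 says "only the AEs with maximum relationship will be accounted" and the footnote to Table 3.2.5 says "only the AEs with maximum severity will be accounted". For the overall Total lines of Table 3.2.5, "E displays the number of all AEs episodes with appropriate severity in the study"; Table 3.2.3 has the matching sentence for relationship. Tables 3.2.4 and 3.2.6 (serious events) are built in the same way.

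Tables 3.2.1, 3.2.3 and 3.2.5 define the episode count identically: "E: the number of AE episodes, which have an appropriate SOC and/or PT". Table 3.2.1 has no worst-grade filter, and its Total line shows patients with at least one event "as well as the total number of AE episodes in the study".

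Protocol 9.13.8 applies the worst-severity and most-related rule to patients. It says nothing about leaving out episodes.

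**The concern.** Counting each patient once at the worst grade is standard for n and is what the protocol asks for. Applying the same filter to an episode count is a different matter, because an episode count is meant to show how often something happened. The filter also works in one direction. It can remove a mild episode when the patient has a worse one of the same term, or an unrelated episode when the patient has a related one, but never the reverse. Within a term, the episode mix can therefore only shift towards more severe and more drug-related.

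Tolerability is a secondary objective, and these tables are its planned breakdown by severity and relationship. Someone checking Table 3.2.5 against Table 3.2.1 would find episodes of the same term missing, under a footnote that says none should be.

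**Working it through.** The plan states no AE figure to reproduce, so the check applies the two written rules to the same events. All event data below are assumed.

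**1. Does the rule filter events or only patients?** SAP 10.2 handles patients in its own sentence. If the preceding sentence also concerned only n, it would add nothing, and its exception for the Total category would have no purpose. The footnotes have the same structure: first which events are accounted for, then that each patient is counted once. The filter therefore acts on E.

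**2. One patient, one term.** Take three mild headaches and one severe headache.

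- Table 3.2.1, headache: E = 3 + 1 = 4.
- Table 3.2.5, headache lines: Severe 1, Moderate 0, Mild 0; sum 1.
- Table 3.2.5, overall Total lines: Severe 1, Mild 3; sum 4.
- Table 3.2.5, Total line inside the headache block: 1 if it is filtered, 4 if it is not. If it is 4, the severity lines above it add up to only 1.

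**3. Nine episodes in three patients.** Patient 1: diarrhoea mild, mild and moderate; nausea mild. Patient 2: nausea severe and mild; headache mild. Patient 3: headache moderate, twice.

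| Row | E, Table 3.2.1 | E summed over severity lines, Table 3.2.5 as written |
|---|---|---|
| Diarrhoea | 3 | 1 |
| Nausea | 3 | 1 + 1 = 2 |
| Headache | 3 | 1 + 2 = 3 |
| Sum of PTs | 9 | 6 |
| Overall Total | 9 | 5 mild + 3 moderate + 1 severe = 9 |

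Headache agrees because neither patient had headaches of differing grade. Diarrhoea loses two mild episodes and nausea one.

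The SOC rows depend on the reading. If the filter takes the patient's worst event across all PTs in the SOC, the gastrointestinal row shows 2 against 6 in Table 3.2.1, and is below the sum of its own PT rows (1 + 2 = 3). If the filter acts only within a PT and the SOC row adds up its PTs, the row shows 3.

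In the overall Total block the Mild line has n = 0 and E = 5, so the plan already accepts different bases for n and E there.

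**4. How large could the shortfall be?** Suppose a patient has k episodes in one category, with grades independent of one another. An episode of grade g is kept only if the other k − 1 are no higher, so

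expected share dropped = 1 − Σ p_g · F_g^(k−1),

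where p_g is the probability of grade g and F_g the probability of grade g or lower.

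- k = 1: 1 − Σ p_g = 0.
- Severity mix 0.90/0.09/0.01 (mild/moderate/severe), k = 2: 1 − (0.81 + 0.0891 + 0.01) = 0.09.
- Severity mix 0.50/0.35/0.15, k = 4: 1 − (0.0625 + 0.2149 + 0.15) = 0.57.
- Relationship with share p related: 1 − p − (1 − p)^k. For p = 0.1, k = 2 this is 0.09; for p = 0.3, k = 4 it is 0.46.

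Across the assumed mixes with k = 2 to 4, the range is about 9% to 57% for severity and 9% to 46% for relationship. These shares apply to a category in which one patient already has 2 to 4 episodes. They are not estimates for the study.

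**5. With E counted at each episode's own grade.** In the data of step 3, the E values of Table 3.2.5 become diarrhoea 3, nausea 3, headache 3; gastrointestinal 6, nervous system 3; Total 9. All equal Table 3.2.1, and n is unchanged.

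**The case against.** The strongest reply is that nothing the protocol requires is affected. Protocol 9.13.8 asks for numbers of patients by severity and relationship, and SAP 3.2 defines the variable as the number and percentage of patients. Both are right as planned, and E in these tables is an addition. Full episode counts by term appear in Tables 3.2.1 and 3.2.2, the overall Total lines give the unfiltered mix by severity and relationship, and all events are listed. The filter is disclosed under the shells. It also keeps n and E on one basis within a PT row, and in a descriptive single-arm study of 60 patients a worst-case display errs on the cautious side. All of this stands, and it limits the weight of the point.

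It does not remove the mismatch. A footnote that discloses a filter beside a definition of E without one leaves E with two meanings.

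A reader might infer more than the documents support:

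- *The Total line inside a PT block must also be too low.* SAP 10.2 exempts the Total category without saying whether that covers the Total line in each block or only the overall one.
- *SOC rows drop events across different PTs.* The general wording allows this, but the footnotes illustrate only events with the same SOC and PT. It is one reading.
- *Tolerability will be misreported.* Patient incidence is untouched, and the shortfall is zero unless a patient has mixed grades or relationships within a category. For serious events it is probably negligible: in the 60-patient reference study described in protocol section 7, one patient had one.

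**Conclusion.** The point holds as a fault in the definition and consistency of E, with modest weight. In the SOC and PT rows of Tables 3.2.3–3.2.6, E as written is not the quantity its footnote states. Where a patient has mixed severity or relationship within a PT, the lines for that term omit the milder or unrelated episodes and do not reconcile with Tables 3.2.1 and 3.2.2 or with the overall Total lines. Whichever reading of the Total line inside each block is right, something fails to add up: either that line differs from Table 3.2.1, or the lines above it do not sum to it.

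The size is unknown, because the documents give no AE counts, and the percentages above rest on assumed mixes and independence. Patient counts, percentages, Tables 3.2.1 and 3.2.2 and the overall Total lines are unaffected.

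**What to change.** Apply the worst-severity and strongest-relationship rule to n only. Count E over all treatment-emergent episodes, each at its own severity or relationship, at Total, SOC and PT level. E in every Total line of Tables 3.2.3 and 3.2.5 then equals Table 3.2.1, and in Tables 3.2.4 and 3.2.6 it equals Table 3.2.2.

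Amend the rule in SAP 10.2 and the footnotes to Tables 3.2.3 and 3.2.5. State there that n is by worst grade and E by own grade, since a row such as Mild 0 / 3 becomes possible; step 2 of the working would produce one.

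The cost is a few sentences of SAP text and a simpler count in the program. The one drawback is that n and E within a SOC or PT row no longer share a basis, as is already the case in the overall Total lines.

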10.3 Pregnancies

Female subjects will be tested for pregnancy at each study visit. The results of these tests and pregnancies episodes will be reported in the listing.

10.4 Clinical laboratory evaluations

Clinical laboratory evaluations include the following parameters:

- hematology results;
- blood chemistry results.

The following parameters, which are evaluated at each study visit, will be analyzed in tables and presented in listings:

- hematology:
 - hemoglobin;
 - platelets;
 - prothrombin time (seconds);

P16-253 (CITRIN) _ STATISTICAL ANALYSIS PLAN _ FINAL 2.0 _ 16 Mar 2018

- prothrombin time (INR);
- blood chemistry:
 - ALT;
 - AST;
 - GGT;
 - total bilirubin;
 - alpha-1-fetoprotein;
 - albumin;
 - creatinine;
 - creatinine clearance.

The results of clinical laboratory evaluations statistical analysis will be represented in accordance with section 7.1 as the following outputs:

- tables with descriptive statistics of measurement values and changes from baseline (visit 1);
- frequency tables of out of range and clinically significant evaluates will be presented;
- shift tables based on clinical evaluation of measurements at visit 1.

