9.13.7 Clinical Laboratory Data

All reported clinical laboratory test results will be assigned to one of the time points using the time windows specified in the table below.

Table 1 - Analysis Time Windows

Time point	Time Window
Visit 1	Last value prior to start of study treatment (i.e. ≤study day 1)
Actual EoT	Study day of last dose (28 days prior to EoT - 14 days post EoT)
12 weeks (day 85 post EoT)	57 – 112 post EoT

Mean changes from baseline to each post-baseline visit will be summarized descriptively.

Laboratory data values collected during the treatment period will be categorized as low, normal, or high based on reference ranges used in this study. The number and percent of patients who experience post-baseline shifts during treatment in clinical laboratory values from low/normal to high and high/normal to low based on the reference range will be summarized.

Additional details of the analyses of clinical laboratory data will be specified in the SAP.

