10.5 Other safety measures

No other safety measures will be analysed in this study.

P16-253 (CITRIN) _ STATISTICAL ANALYSIS PLAN _ FINAL 2.0 _ 16 Mar 2018

11 Pharmacokinetics

No pharmacokinetic and pharmacodynamic parameters will be analyzed in this study.

12 Other analyses

No other analyses will be performed in this study.

13 Interim analyses and data monitoring

No interim analysis is planned for this study.

14 Technical details and reporting conventions

Statistical analysis will be performed using SAS 9.4. One (final) statistical analysis report will be prepared in the Microsoft Office Word (.docx) format after the end of data collection and database lock. The results of statistical analysis will be presented in the form of tables, figures and listings in English.

15 Summary of changes to the Protocol

This SAP is fully consistent with the clinical study Protocol.

16 List of TFLs**16.1 Tables****Subjects Disposition**

Table 1.1 – Subjects Dispositions
Table 1.2 – The reasons of early withdrawal
Table 1.3 – Violation of eligibility criteria

Demographics and anthropometric characteristics

Table 1.4.1 – Demographics and anthropometric characteristics [CP]
Table 1.4.2 – Demographics and anthropometric characteristics (prior treatment groups) [CP]
Table 1.4.3 – Demographics and anthropometric characteristics (treatment-experienced groups) [CP]
Table 1.4.4 – Demographics and anthropometric characteristics (Child Pugh score groups) [CP]
Table 1.4.5 – Demographics and anthropometric characteristics [TP]
Table 1.4.6 – Demographics and anthropometric characteristics [SP]
Table 1.5.1 – CHC disease characteristics [CP]
Table 1.5.2 – CHC disease characteristics (prior treatment groups) [CP]
Table 1.5.3 – CHC disease characteristics (treatment-experienced groups) [CP]
Table 1.5.4 – CHC disease characteristics (Child Pugh score groups) [CP]
Table 1.5.5 – CHC disease characteristics [TP]
Table 1.5.6 – CHC disease characteristics [SP]

CHC disease characteristics

Table 1.6.1 – Liver fibrosis stage [CP]
Table 1.6.2 – Liver fibrosis stage (prior treatment groups) [CP]
Table 1.6.3 – Liver fibrosis stage (treatment-experienced groups) [CP]
Table 1.6.4 – Liver fibrosis stage (Child Pugh score groups) [CP]
Table 1.6.5 – Liver fibrosis stage [TP]
Table 1.6.6 – Liver fibrosis stage [SP]

Liver fibrosis stage

P16-253 (CITRIN) _ STATISTICAL ANALYSIS PLAN _ FINAL 2.0 _ 16 Mar 2018

Alcohol consumption

Table 1.7.1 – Alcohol consumption [CP]

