N: the number of patients in the safety population.

n: the number of valid measurements.

SD: standard deviation.

IQR: interquartile range.

EoT: end of treatment.

SVR12: sustained virological response at 12 weeks after end of treatment.

Table displays descriptive statistics for general blood test parameters values and their changes from baseline (visit 1).

Program code, date, time

Data extracted: DD.MM.YYYY

P16-253 (CITRIN) _ STATISTICAL ANALYSIS PLAN _ FINAL 2.0 _ 16 Mar 2018

 AbbVie LLC
 P16-253 (CITRIN)

Table 3.3.2 Hematology. Clinical assessments

 The safety population
 Page X of X

 Parameter
 Visit
 Value

 Total
 (N = XX)

Hemoglobin

Visit 1

| | |
|--------------|-----------|
| n | XXX |
| Normal | XX (XX.X) |
| Abnormal NCS | XX (XX.X) |
| Abnormal CS | XX (XX.X) |

EoT

| | |
|--------------|-----------|
| n | XXX |
| Normal | XX (XX.X) |
| Abnormal NCS | XX (XX.X) |
| Abnormal CS | XX (XX.X) |

SVR12

| | |
|--------------|-----------|
| n | XXX |
| Normal | XX (XX.X) |
| Abnormal NCS | XX (XX.X) |
| Abnormal CS | XX (XX.X) |

P16-253 (CITRIN) _ STATISTICAL ANALYSIS PLAN _ FINAL 2.0 _ 16 Mar 2018

| Parameter | Total |
|-----------|----------|
| Visit | (N = XX) |
| Value | |

Platelets

...

Prothrombin time

...

N: the number of patients in the safety population.

n: the number of valid measurements. Percentages are based on the number of valid measurements at analyzed visit.

CS: clinically significant.

NCS: not clinically significant.

EoT: end of treatment.

SVR12: sustained virological response at 12 weeks after end of treatment.

Program code, date, time

Data extracted: DD.MM.YYYY

P16-253 (CITRIN) _ STATISTICAL ANALYSIS PLAN _ FINAL 2.0 _ 16 Mar 2018

 AbbVie LLC
 P16-743 (CITRIN)

Table 3.3.3 Hematology. Shift table

 The safety population
 Page X of X

| Parameter | Baseline (visit 1) | | | Total assessed |
|----------------|--------------------|-----------|--------------|----------------|
| | Visit | Normal | Abnormal NCS | |
| Value | | | | |
| Hemoglobin | | | | |
| Visit 1 | | | | |
| Normal | | | | XX (XX.X) |
| Abnormal NCS | | | | XX (XX.X) |
| Abnormal CS | | | | XX (XX.X) |
| Total assessed | | | | XX (100) |
| EoT | | | | |
| Normal | XX (XX.X) | XX (XX.X) | XX (XX.X) | XX (XX.X) |
| Abnormal NCS | XX (XX.X) | XX (XX.X) | XX (XX.X) | XX (XX.X) |
| Abnormal CS | XX (XX.X) | XX (XX.X) | XX (XX.X) | XX (XX.X) |
| Total assessed | XX (100) | XX (100) | XX (100) | XX (100) |
| SVR12 | | | | |

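### The SAP's laboratory shift tables use Normal / Abnormal NCS / Abnormal CS, so the counts of patients shifting to high or to low that the protocol requires cannot be obtained from them

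*SAP*

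**What the plan says.** Protocol section 9.13.7 sets the categories: "Laboratory data values collected during the treatment period will be categorized as low, normal, or high based on reference ranges used in this study". It then asks for the number and percent of patients with "post-baseline shifts during treatment in clinical laboratory values from low/normal to high and high/normal to low based on the reference range". What it leaves open is limited: "Additional details of the analyses of clinical laboratory data will be specified in the SAP".

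SAP section 10.4 plans three kinds of laboratory output:
- descriptive statistics of values and of changes from Visit 1;
- frequency tables of out-of-range and clinically significant results;
- "shift tables based on clinical evaluation of measurements at visit 1".

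The shells in SAP section 18 show what this means in practice. "Table 3.3.3 Hematology. Shift table" crosses the Visit 1 category with the category at EoT and at SVR12, and the categories are Normal, Abnormal NCS (not clinically significant) and Abnormal CS (clinically significant). Frequency shell 3.3.2 uses the same three. Blood chemistry tables 3.4.1 to 3.4.3 are to be built in the same way. No planned table has a low or high category.

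SAP section 15 states: "This SAP is fully consistent with the clinical study Protocol". For laboratory data, the revision history of version 2.0 mentions only that the time windows were moved to another section.

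**The concern.** The protocol asks for a directional summary against an external yardstick, the reference range. The SAP replaces it with a classification by clinical significance, in which a result is abnormal without being high or low. A patient whose platelets rise above the range and one whose platelets fall below it can land in the same cell.

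Tolerability is a secondary objective, and the study has one treatment group, so no comparator helps to interpret a cell that pools rises and falls. The change is also undeclared. SAP section 2 says that departures from the finalized SAP will be explained in the study report, but that rule does not cover departures of the SAP from the protocol. The required summary could therefore drop out of the report without comment.

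**Working it through.** The plan gives no figure to reproduce. The check maps the protocol's categories onto the SAP's grid.

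**Inputs.** Protocol 9.13.7: three categories (L, N, H), hence 3 × 3 = 9 possible transitions. It counts four of them: N→H and L→H (to high), N→L and H→L (to low). SAP shell 3.3.3: three categories (Normal, NCS, CS), hence 9 cells. Assumption: Normal in the SAP means within the reference range, and both abnormal categories mean outside it.

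**Mapping.**

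| Protocol transition | SAP cells where it falls |
|---|---|
| N→N | Normal→Normal (1 cell) |
| **N→H**, **N→L** | Normal→NCS or Normal→CS (2 cells) |
| L→N, H→N | NCS→Normal or CS→Normal (2 cells) |
| **L→H**, **H→L**, L→L, H→H | NCS or CS → NCS or CS (4 cells) |

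Transitions: 1 + 2 + 2 + 4 = 9. Cells: 1 + 2 + 2 + 4 = 9. Of the four transitions in bold, none has a cell of its own. In a Low / Normal / High grid, all four do.

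**What can still be said from the SAP grid.** Let a be the number of patients in the two Normal→Abnormal cells and b the number in the four Abnormal→Abnormal cells. Write U for the protocol's count to high and D for its count to low.
- NH + NL = a, and LH + HL lies between 0 and b.
- So U = NH + LH lies anywhere from 0 to a + b, and so does D = NL + HL.

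Example with assumed counts: 60 patients assessed, a = 10, b = 0. Then U can be anything from 0 to 10 (0% to 10/60 = 16.7%), with D = 10 − U. Ten patients going N→H and ten going N→L would give identical SAP tables if they were judged equally significant.

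**Whether another output fills the gap.**
- Shell 3.3.2 and its chemistry copy 3.4.2 use the same three categories, so the out-of-range frequencies are not split by direction.
- Tables 3.3.1 and 3.4.1 give group statistics for the change from baseline. They show direction for the group but not how many patients crossed a range limit.
- Listings 4.4 and 4.5.1 give individual results, not a number and percent.

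**Period.** The protocol's shifts are those on treatment. The shells tabulate EoT and SVR12. SVR12 is post-treatment, and the additional on-treatment visits allowed by Protocol 9.1 have no row.

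**Scope.** SAP 10.4 lists 4 hematology and 8 chemistry parameters, 12 in all. If a parameter can be abnormal in one direction only, the Normal→Abnormal cells do give the protocol's count. Protocol 9.8 names an upper limit of normal for ALT and AST and for no other parameter, so for those two abnormal may in practice mean high.

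**The case against.** The strongest case on the other side has three parts.

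*The protocol delegates detail to the SAP.* It does, but for additional details. Replacing the required categories is more than adding detail, and section 15 does not record it.

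*The low/normal/high table may not be feasible.* It needs both range limits from each local laboratory, and the documents name only an upper limit, for ALT and AST. SAP version 2.0 is dated March 2018, after the planned end of data collection on 10 December 2017, so limits that were not collected may be out of reach. This stands, and the fix has to be conditional on it. On the other side, Protocol 9.13.7 presupposes reference ranges, and the SAP's own out-of-range tables need them.

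*The stakes are modest.* This is a descriptive safety table in a single-arm study of 60 patients. That also stands.

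A reader might infer more than the documents support:
- That each investigator judges significance. The SAP refers to clinical evaluation and to NCS/CS but does not name the assessor or the rule.
- That the direction of change cannot be read at all. The change-from-baseline tables and the listings show it. What is missing is the patient count.
- That a high-to-low move appears as no shift. Such a patient can move between NCS and CS. Only the direction is lost.
- That harmful and beneficial shifts are mixed throughout. Normal-to-abnormal and abnormal-to-normal have separate cells. The ambiguity arises only where both directions are possible.
- That the reference trial's 22% with platelets below 90 × 10⁹/L and 17% with albumin below 3.5 g/dL measure the loss. These are baseline cut-offs from another cohort, not reference limits, and a patient who stays low makes no shift under the protocol either.

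**Conclusion.** The point holds as an undeclared inconsistency between protocol and SAP. The number and percent of patients shifting to high and to low, which Protocol 9.13.7 requires, cannot be obtained from the planned shift or frequency tables: 0 of the 4 relevant transitions are identifiable. The layout applies to all 12 parameters. The loss is clearest for those that can be abnormal either way, such as hemoglobin and platelets, and may be small or nil for ALT and AST. The documents do not allow an estimate of how many patients would be affected.

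The conclusion rests on reading Normal and Abnormal in the shells as inside and outside the reference range. If the SAP means something else, the tables are further still from the protocol. Neither the SVR12 analysis nor adverse event reporting is touched. The point should be corrected, but it does not bear on the primary result.

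**What to change.** 1. Recast shells 3.3.3 and 3.4.3 as Low / Normal / High by the reporting laboratory's reference range, baseline against on-treatment/EoT value. Say how values from additional on-treatment visits enter. Show SVR12 separately, labelled post-treatment.
2. Add two summary rows per parameter, low/normal to high and high/normal to low, each with n (%).
3. Count values without a recorded range as not classified, and show that count.
4. Keep the NCS/CS categories in frequency tables 3.3.2 and 3.4.2 as supplementary output.
5. Confirm which range limits the CRF collected. For any parameter where they were not collected, replace the blanket statement in SAP section 15 with an explicit note of the departure from Protocol 9.13.7.

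The cost is reprogramming two tables. Some values will be unclassified. If few laboratories supplied both limits, these could be numerous for some parameters, and step 5 then carries the weight.
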